6.2.2.2 AMG 176 Management of Toxicities

6.2.2.1 Management of Anemia

Anemia is one of the MM- and AML-related organ/tissue dysfunction and is generally related to bone marrow infiltration or renal dysfunction. In AML, patients often present with a normocytic, normochromic anemia which worsens with chemotherapy. Subjects should be monitored for changes in hemoglobin as described in the schedule of assessments (see Section [1.3](#)). Increased monitoring should be implemented in subjects whose hemoglobin < 8 g/dL. Subjects should have anemia corrected in accordance with the local practice and institutional guidelines. Hemoglobin parameters of grade 3 but not considered as clinically relevant (ie, without symptoms of anemia and not leading to a clinical intervention including withdrawal of investigational product treatment, transfusion, or significant additional concomitant therapy) will not require discontinuation of AMG 176. A sudden decrease in hemoglobin levels requires the investigation of hemolysis. Treatment should be discontinued for persistent (ie, ongoing > 3 weeks after the end of a treatment cycle) grade 3 or 4 anemia in the absence of detectable MM or AML which may reflect a prolonged marrow toxic effect of AMG 176.

6.2.2.2 Management of Infections

Subjects with evidence of existing infection should be closely monitored while being treated with AMG 176. Subjects with active systemic infections requiring IV antibiotics, antivirals, or antifungals should not be dosed with AMG 176 until infection has resolved and if being treated with an anti-infectious therapy, the course of such therapy should have been completed. Management should be tailored to the appropriate prophylaxis and/or treatment for the underlying infection according to the local SOC and institutional guidelines with the exception of excluded medications detailed in Section [6.1.7](#).

Infection Prophylaxis

Subjects who may experience neutropenia are at a high risk for infectious complications. As appropriate, these subjects should be administered prophylactic antibacterial and antifungal per institutional guidelines.

These subjects should be monitored for early signs of breakthrough infections after the initiation of antibacterial therapy to prompt additional evaluation and possible therapy

modification. Subjects experiencing diarrhea should be closely monitored for their electrolyte levels.

6.2.2.2.3 Management of Cardiac Arrhythmia

Subjects with risk factors for, or evidence of, existing heart disease should be closely monitored throughout their treatment with AMG 176. Subjects should be clinically monitored on ongoing basis for cardiac function (blood pressure, heart rate, ECHO, and ECG) according to the schedule of assessments (see Section 1.3). The administration of AMG 176 should be withheld if grade 3 or 4 arrhythmias (including tachycardia) develop or appear to be exacerbated by AMG 176 treatment. For any grade 3 arrhythmia related to AMG 176 administration, the AMG 176 dose should be reduced. Treatment may be resumed once the signs and symptoms resolve to baseline value or grade 1. Management should be tailored to the appropriate treatment for the underlying cardiac disorder according to the local SOC and institutional guidelines. For any grade 4 arrhythmia related to AMG 176 administration, AMG 176 should be permanently discontinued.

6.2.2.2.4 Management of Renal Toxicities

Renal dysfunction is one of the MM-related organ/tissue dysfunction. Renal function must be monitored closely during treatment with AMG 176. Serum chemistry values, including blood urea nitrogen (BUN), serum creatinine, and urine for urinalysis and microscopic exam (microscopic exam only needed for positive dipstick), must be obtained and reviewed prior to each dose of AMG 176 per the schedule of assessments (see Section 1.3). AMG 176 must be held for subjects with CrCl or estimated glomerular filtration rate $< 30 \text{ mL/min}/1.73 \text{ m}^2$ or any other grade 3 or 4 renal toxicity any time during study treatment participation. Management should be tailored to the appropriate treatment for the underlying renal disorder according to the local SOC and institutional guidelines. AMG 176 can be restarted when the toxicity has improved to at least a grade 2.

6.2.2.2.5 Management of Gastrointestinal Toxicities

Gastrointestinal toxicity (vomiting and diarrhea) have been observed with the use of AMG 176. AMG 176 must be withheld from subjects with grade 3 or 4 gastrointestinal toxicity at any time during study treatment participation. Management should be tailored to the appropriate treatment according to the local SOC and institutional guidelines. AMG 176 can be restarted when the toxicity has improved to at least a grade 2.

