6.2.2 Dosage Adjustments, Delays, Rules for Withholding or Restarting, Permanent Discontinuation

6.2.2.1 Amgen Investigational Product: AMG 176

The reason for dose change of AMG 176 is to be recorded on each subject's CRF(s).

Dosage Adjustments

Upon completion of the ramp-up dosing if applicable, the subject should continue on the same target dose of AMG 176 throughout the study unless the following events occur:

- For subjects experiencing an adverse event meeting the DLT definition or intolerable related adverse events BUT showing evidence of response, there will be an option to reduce the dose to the immediate next lower dose level shown to be safe and tolerable in the dose escalation part of the study.
 - The study drug can be resumed once the adverse events recover to baseline or grade 1 and the reintroduction of AMG 176 is deemed safe by the site investigator and Amgen's Medical Monitor.
 - Subjects must be informed of the risk of continuing on therapy. Each subject is only allowed a single dose reduction. Subjects showing evidence of response or subjects who in the opinion of the investigator may be responding to AMG 176, may have the option to have more than single dose reduction if deemed safe by the site investigator and Amgen's medical monitor.
- Subjects who experience grade 3 arrhythmia possibly associated with AMG 176, AMG 176 dosing must be resumed at the immediate next lower dose level if the requirements mentioned below in Rules for Restarting are met.
- For subjects meeting the withholding criteria for elevation of cardiac troponin (> 0.1 ng/mL), AMG 176 dosing can be resumed at the immediate next lower dose level if the requirements mentioned below in Rules for Dose Withholding are met.

Subjects should not be re-challenged with AMG 176 if the following AMG 176-related adverse events occur:

- Any life-threatening adverse events
- Drug-induced liver injury (DILI) meeting Hy's law
- Persistent grade 3 adverse events that do not recover to baseline or grade 1 within 4 weeks.
- Any AMG 176 related adverse event meeting DLT-criteria that recurs despite 2 dose level reductions

Dosage Delays

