During the DLT evaluation period, if the dosing is delayed for more than 2 weeks the subject will be removed from the study and will be replaced. After DLT evaluation period, if the dosing is delayed for < 4 weeks, the subject should resume the treatment as soon as possible if deemed safe by the investigator. The investigator should inform the Amgen Clinical team as soon as the unexpected dosing interruption occurs. If the dosing of AMG 176 is delayed > 4 weeks (missing 1 cycle) due to AMG 176 related adverse events, the subject will be permanently removed from AMG 176 treatment. If the dosing delay occurred under conditions other than those associated with AMG 176 related toxicities, the case will be reviewed by Amgen medical monitor to determine whether the subject will be allowed to resume AMG 176 treatment.

Rules for Dose Withholding

AMG 176 should be withheld for any of the following:

- Suspected DLT (including adverse events that meet DLT definition outside DLT observation period).
- Aspartate aminotransferase or ALT greater than $3 \times$ ULN or total bilirubin greater than $1.5 \times$ ULN.
- Any grade 3 arrhythmia deemed possibly related to AMG 176. Should dosing be resumed, AMG 176 should be given at the next lower dose level.
- Any central lab elevation of cardiac troponin > 0.1 ng/mL (ADVIA Centaur XP manufacturer's prognostic cut-off) OR any change in the clinical status, above lab analytes (central or locally obtained), echocardiogram, or ECG deemed significant by the investigator or study subjects' care team.
- Upon meeting withholding criteria for AMG 176, investigator/site physician should evaluate appropriateness of apparent benefit vs risk of re-initiating AMG 176. Based on the assessment, a subject may be continued drug at a reduced dose or permanently discontinue therapy.
 - Low elevations from 0.04 ng/mL for females or 0.059 ng/mL for males to ≤ 0.1 ng/mL do not require withholding or dose reductions, though troponins should be monitored with subsequent doses.

- Elevations > 0.1 ng/mL should result in a dose withholding, and if further treatment is considered, should be restarted at one dose level below the dose where elevated troponins were observed
- Any consideration for continued treatment of AMG 176 after troponin elevations will require discussion between the investigator, subject, and Amgen medical monitor, and following normalization of all abnormalities.

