- Study subjects that meet withholding criteria require continuous cardiac monitoring (telemetry) for at least 24 hours, and a cardiologist's evaluation that includes transthoracic echocardiography to assess the study subject and provide recommendations for further cardiac care. Monitoring should continue according to local SOC.

Rules for Restarting

AMG 176 dosing can be resumed:

- If the adverse event resolves to grade ≤ 1 or return to subjects' baseline values.
- For subjects meeting the withholding criteria for elevation of cardiac troponin (> 0.1 ng/mL), AMG 176 dosing can be resumed at the immediate next lower dose level if the requirements mentioned above in Rules for Dose Withholding are met.
- If the restarting of therapy should be deemed safe by the site investigator and Amgen's medical monitor.

Rules for Permanent Discontinuation

Subjects will permanently discontinue from the investigational product if the following are observed:

- Subjects experience adverse events meeting the DLT criteria at any time. Subjects will be followed until the DLT is resolved, returns to baseline value or is considered stable. Subjects will be withdrawn from AMG 176 treatment and will be treated as deemed appropriate by the investigator or treating physician. Except for:
 - Subjects showing evidence of response or subjects who in the opinion of the investigator may be responding to AMG 176, may have the option to continue therapy once the adverse events recover to baseline or grade 1 and the re-introduction of AMG 176 is deemed safe by the investigator, and Amgen's medical monitor. The subject should restart at a reduced dose.
 - Intolerance of AMG 176
 - Grade 3 central laboratory elevations of troponin
 - Any grade 4 arrhythmias possibly associated with AMG 176
 - Symptoms of clinically significant cardiac dysfunction, ECG changes, or diagnostic evidence of decreased cardiac function or cardiac injury irrespective of any cardiac troponin level (centrally or locally obtained). Study subjects that meet permanent discontinuation criteria require continuous cardiac monitoring (telemetry) for at least 24 hours, and a cardiologist evaluation that includes transthoracic echocardiography to assess the study subject and provide

recommendations for further cardiac care. Monitoring should continue according to local SOC.

- Hepatotoxicity (as defined in Section [11.7](#))
- The dosing is delayed > 4 weeks due to AMG 176-related adverse events

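### The renal and GI toxicity sections allow AMG 176 to restart at grade 2 without excluding events that Section 6.2.2.1 bars or restricts, and nothing says which rule governs

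*Protocol*

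**What the plan says.** Protocol Sections 6.2.2.2.4 and 6.2.2.2.5 require AMG 176 to be held for grade 3 or 4 renal or GI toxicity at any point during treatment. The renal section adds creatinine clearance or estimated filtration rate below 30. Both close with the same sentence: "AMG 176 can be restarted when the toxicity has improved to at least a grade 2". Neither mentions attribution, DLT status, grade 4 severity, duration or dose reduction.

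Section 6.2.2.1 has three sets of rules that reach the same events:

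- **Permanent discontinuation.** One trigger is "Subjects experience adverse events meeting the DLT criteria at any time". The exception covers subjects with evidence of response and subjects who, in the investigator's view, may be responding. They must first recover to baseline or grade 1, and "The subject should restart at a reduced dose". Dosage Adjustments sets the same recovery level for responders: "The study drug can be resumed once the adverse events recover to baseline or grade 1".
- **No rechallenge.** This list is limited to AMG 176-related events. It includes life-threatening events and grade 3 events that have not reached baseline or grade 1 by 4 weeks.
- **Restarting.** The first bullet begins "If the adverse event resolves to grade" 1 or lower and offers return to baseline as the alternative. The last bullet asks for a safety judgment by the site investigator and the sponsor's medical monitor.

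The arrhythmia section (6.2.2.2.3), also organ-specific, carries the general limits over. It says "Treatment may be resumed once the signs and symptoms resolve to baseline value or grade 1" and "For any grade 4 arrhythmia related to AMG 176 administration, AMG 176 should be permanently discontinued".

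**The concern.** An investigator managing diarrhea or renal injury will look in the section on that organ, which gives a complete hold-and-restart instruction with no pointer to the stricter rules. Followed as written, it would allow re-dosing at residual grade 2 and unchanged dose in a subject whom Section 6.2.2.1 removes from AMG 176, or readmits only at a lower dose after fuller recovery. Two sites could also treat the same event differently.

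The stake is patient safety, in organs where the protocol already sees risk. Intestinal epithelial damage was linked to the deaths in the rat and dog studies (Section 2.2.2.3), and GI toxicity is a listed potential risk (Section 2.3.2.3). Impaired renal function may raise the risk of tumor lysis syndrome, which was fatal in 1 of 109 safety-evaluable subjects (Section 2.3.2.1).

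**Working it through.** The protocol gives no figure of its own to reproduce, so the main check is a comparison of rules.

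**Step 1: which renal and GI events meet DLT criteria in AML (Table 6-1, related events).** A non-hematologic event of grade 3 or higher that is not clearly due to the leukemia is a DLT unless exempt. The exemptions include no renal injury, only brief, clinically insignificant isolated electrolyte abnormalities, so most related grade 3–4 renal events qualify. The GI exemptions cover grade 3 only:

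- diarrhea that falls to grade 2 or lower in under 72 hours;
- nausea and vomiting on the same time limit, provided no tube feeding, parenteral nutrition or prolonged hospital stay is needed;
- constipation that falls to grade 2 or lower within 7 days.

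Other related grade 3 GI events, and grade 4 GI events, are DLTs whatever their duration.

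**Step 2: apply both rule sets to the same subject.**

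| Case | Organ section | Section 6.2.2.1 |
|---|---|---|
| Related grade 3 diarrhea for 5 days despite optimal support, now grade 2 | Restart allowed, no dose change mentioned | Meets DLT criteria: discontinue; if responding or possibly responding, wait for baseline or grade 1 and reduce the dose |
| Related life-threatening grade 4 renal event, now grade 2 | Restart allowed | No rechallenge |
| Related grade 3 event that remains at grade 2 beyond 4 weeks (baseline grade 0–1) | Restart allowed | No rechallenge; if dosing is still held, the rule on related delays over 4 weeks also removes the subject |
| Grade 3 diarrhea down to grade 2 within 48 hours (not a DLT), baseline grade 0–1 | Restart allowed | First restart bullet requires grade 1 or baseline |

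In the last case the rules differ only because baseline was below grade 2. With a grade 2 baseline they agree.

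**Step 3: look for a precedence rule.** Sections 6.2.2.1, 6.2.2.2.4 and 6.2.2.2.5 contain none, and the two organ sections do not refer back to 6.2.2.1.

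**Step 4: what can be said about size.** The documents give no rate of grade 3–4 renal or GI events. Section 2.1 reports no DLTs among 11 + 22 = 33 subjects in Parts 3b and 4 by November 2022. The exact one-sided 95% upper bound is 1 − 0.05^(1/33) = 0.0868, or 8.7%. It refers to any DLT, pools doses, counts enrolled rather than DLT-evaluable subjects (fewer evaluable would raise it), and covers only the evaluation period. The discontinuation rule has no such time limit. Planned enrollment in the parts open at Amendment 16 is 11 + 60 + 68 = 139, against 36 + 12 + 17 + 11 + 4 = 80 in closed parts, total 219 (Section 4.2). That is a planned number, not a count of subjects exposed to the conflict.

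**The case against.** The best reply is that the rules can be obeyed together. The organ sections are permissive and concern subjects on hold, whereas a subject who is permanently discontinued or barred from rechallenge is no longer on hold. On that reading only the grade 2 versus grade 1 threshold conflicts. The reading is reasonable, but the protocol does not state it.

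A second reply is that organ-specific rules are normal here and should govern. The anemia paragraph sets its own stopping rule, and the arrhythmia section may only repeat arrhythmia rules already in 6.2.2.1. This is a fair defense of grade 2 as a deliberate threshold. Carried through, however, it would cancel the bar on rechallenge after life-threatening events for two organ systems, and nothing suggests that was meant.

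Third, Section 6.2.2.1 has safeguards. The investigator and medical monitor judge the safety of restarting. When withholding criteria are met, a benefit-risk step leads to a reduced dose or discontinuation, although its sub-points concern troponin. The sponsor's clinical team should be told of unexpected interruptions, and a related delay over 4 weeks ends treatment. These count. A reader might infer that sites can re-dose with no sponsor check, and the documents do not support that.

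The safeguards still do not decide which rule applies. The restart bullets are joined by neither 'and' nor 'or'. If any one suffices, a safety judgment alone permits grade 2 restart and the threshold mismatch disappears. If the general conditions are cumulative, grade 1 or baseline is required. On either reading, the organ sections still lack an exclusion for discontinued and no-rechallenge subjects.

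**Conclusion.** The point holds as a conflict of wording with a safety consequence: the renal and GI sections allow grade 2 restart without excluding events that Section 6.2.2.1 treats more strictly, and no text sets precedence. It is minor. It rests on a site reading the organ section literally. The DLT part is probably uncommon in cycle 1, given no DLTs in 33 subjects; how often it would arise in later cycles, or for renal and GI events specifically, cannot be estimated.

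Two stronger readings go too far. A reader might infer that the protocol directs re-dosing of barred subjects. It does not: the organ text permits restart, and the bars remain in force elsewhere. A reader might also infer that DLT counts and dose-finding are compromised. The route is narrow: a grade 3 diarrhea, nausea, vomiting or constipation exempt in AML, followed by a grade 2 residue long and serious enough to become a DLT in its own right. Section 6.2.1.2.1 also has the dose-level review team look at grade 3 or higher toxicities that are not DLTs. No endpoint or analysis is shown to change.

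The study was terminated early (SAP Section 10) and actual enrollment is not given, so the value of a correction lies mainly in any further amendment or later protocol that reuses this text.

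**What to change.** Add to the end of Sections 6.2.2.2.4 and 6.2.2.2.5:

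*The permanent-discontinuation rules, the no-rechallenge list and the dose-reduction requirements in Section 6.2.2.1 prevail. Restart at grade 2 applies only to events that do not meet DLT criteria and are not on the no-rechallenge list, and requires agreement of the investigator and the medical monitor that it is safe.*

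For the remaining non-DLT events, state one restart threshold in both places: either grade 1 or baseline, or grade 2. That is a clinical choice for the sponsor. Simply exempting renal and GI events from the first restart bullet would not be enough. A related grade 3 event restarted at grade 2 in week 2 and still at grade 2 in week 4 would be allowed by the exemption and caught by the persistent-grade-3 bar. If grade 2 is kept, say that a related grade 3 event not at baseline or grade 1 by 4 weeks stops AMG 176. Table 6-1 needs no change.

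The cost is a few sentences, with no new data, visits or subjects. The downside is a slightly stricter restart rule for a few subjects.

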6.2.2.2.6 Prophylaxis and Management of Tumor Lysis Syndrome

Refer to Section [11.8](#) for guidance.

6.2.2.2.7 Management of Troponin and Other Cardiac Enzymes Elevation

Subjects with risk factors for, or evidence of, existing heart disease should be closely monitored throughout their treatment with AMG 176. Subjects should be clinically monitored with local and central cardiac monitoring tests for elevated troponin and cardiac enzymes diagnostic of cardiac injury. Local troponin testing will be performed to guide immediate clinical care. Central testing of troponin-I with ADVIA Centaur XP troponin-I assay will be performed for all screening, grading, and withholding decisions.

6.2.2.8 SARS-CoV-2 and COVID-19 Guidance

Grade	Interruption/Delay	Specific Management	Restart Guidance	Permanent Discontinuation
SARS-CoV-2 infection and COVID-19 disease				
Asymptomatic	Interruption required until at least 10 days since positive SARS-CoV-2 test. UNLESS subject previously fully vaccinated against SARS-CoV-2. If subject previously vaccinated and tests positive, then discuss with medical monitor.	Follow local guidelines and SOC for COVID-19 treatment and isolation Contact Amgen medical monitor within 1 business day to ensure appropriate documentation and management of study activities	
Restart possible upon agreement between investigator and Amgen medical monitor provided:
There are no new findings on physical exam related to SARS-CoV-2, ANDSubject tests negative for SARS-CoV-2 by RT-PCR, ORIf subject continues to test positive for SARS-CoV-2 more than 10 days after initial positive test, or if subject initially tests positive in the setting of prior COVID vaccination, resume investigational product only after discussion with subject and reassessment of individual risk/benefitConsider chest imaging, ECG, ECHO, and cardiology assessment prior to restartConsider hospitalization for restart of IP based on length of treatment interruption, risk of CRS at restart, and amount of time since subject was last treatedDose modification: resume at the same dose or reduce to next lower dose, if clinically indicatedPremedication and assessments: follow guidance in SOA tables	Immediately stop the infusion (if applicable) and permanently discontinue IP therapy, if: Subject required treatment interruption greater than 28 days and upon discussion with Amgen medical monitor the decision is made to permanently discontinue treatment OR Initial benefit/risk assessment for individual subject is not maintained any longer

Page 1 of 2

Abbreviations defined on last page of table.

Grade	Interruption/Delay	Specific Management	Restart Guidance	Permanent Discontinuation
SARS-CoV-2 infection and COVID-19 disease				
Symptomatic	Interruption required until at least 10 days since complete resolution of acute symptoms	Follow local guidelines and SOC for COVID-19 treatment and isolation Contact Amgen medical monitor within 1 business day to ensure appropriate documentation and management of study activities	
Restart possible upon agreement between investigator and Amgen medical monitor provided:
There are no new findings on physical exam and chest imaging, related to SARS-CoV-2Subject tests negative for SARS-CoV-2 by RT-PCR,
ORIf subject continues to test positive for SARS-CoV-2 more than 10 days after initial positive test, resume IP only after discussion with subject and reassessment of individual risk/benefitConsider chest imaging, ECG, ECHO, and cardiology assessment prior to restartConsider hospitalization for restart of IP based on length of treatment interruption, risk of CRS at restart, and amount of time since patient was last treatedDose modification: resume at the same dose or reduce to next lower dose if clinically indicatedPremedication and assessments: follow guidance in SOA tables	Immediately stop the infusion (if applicable) and permanently discontinue IP therapy if: Subject required treatment interruption greater than 28 days due to severe or life-threatening COVID-19 OR Initial benefit/risk assessment for individual subject is not maintained any longer

Page 2 of 2

COVID-19 = coronavirus disease 2019; CRS = cytokine release syndrome; ECG = electrocardiogram; ECHO = echocardiogram; RT-PCR = real-time polymerase chain reaction; SARS-CoV-2 = severe acute respiratory syndrome coronavirus 2; SOA = Schedule of Activities; SOC = standard of care

